Phase 2 Starting Dose Level (DL)	APR-246 4.5 g/patient/day 1.5 g/patient (for first 45 minutes) + 3.0 g/patient (for 5 hours 15 minutes)
First dose reduction DL-1	APR-246 4.0 g/patient/day 1.33 g/patient (for first 45 minutes) + 2.67 g/patient (for 5 hours 15 minutes)
Second dose DL-2*	APR-246 3.5 g/patient/day 1.16 g/patient (for first 45 minutes) + 2.34 g/patient (for 5 hours 15 minutes)

A Simon’s two-stage minimax design will be applied, as follows:

Stage 1: Enroll a total of 24 evaluable patients at the MTD (including patients who were enrolled during the Phase 1 part of the study). If less than 6 of 24 patients achieve CR, then the study will be terminated early with the conclusion that the regimen does not warrant further investigation. If 6 or more patients achieve CR, then enrollment will be permitted to continue to Stage 2.

Stage 2: Enroll 21 more evaluable patients for a total of 45. If less than 14 of 45 patients achieve CR, then there is insufficient evidence to support continued study of this treatment. If 14 of 45 patients achieve CR, then there is sufficient evidence to support further study of APR-246 in combination with azacitidine in Phase 3. Up to 39 additional evaluable patients will be treated at the level of the MTD in the Phase 2 portion of the trial. The maximum total accrual is 51 patients. Disease assessments will occur following 3 cycles of therapy (Figure 3).

[figure not shown]

Figure 3. Phase 2 Schema

b. General Concomitant Medication and Supportive Care Guidelines

In general, the use of any concomitant medications/therapies deemed necessary for the care of the patient are allowed, with specific exceptions below. Prophylactic anti-emetic therapy is permitted where indicated.

Any disease progression that requires other specific anti-tumor therapy will be cause for discontinuation from the trial.

c. Permitted Medications

i. Growth Factors

Erythropoiesis-stimulating agents (ESAs) are not allowed for anemia during the study. G-CSF is allowed during study only in cases of febrile neutropenia where G-CSF can be used for short term.

ii. Anticoagulant Therapy

Subjects who are taking warfarin (or equivalent) may participate in this study; however, it is recommended that prothrombin time (PT-INR) and PTT be monitored carefully at least once per week for the first month, then monthly if the INR is stable. Subcutaneous heparin, low molecular weight heparin and oral anticoagulants are permitted.

iii. QT prolonging Agents

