Patients requiring a dose delay of > 28 days must be permanently discontinued from study drug. Following 4 cycles of therapy for responding patients (i.e. CR, PR, HI, or marrow CR), treatment with APR-246 and azacitidine can be delayed per the study investigator for up to 14 days to allow for count recovery or at investigator discretion post discussion with Moffitt PI. Non-hematologic grade 4 treatment related adverse events will lead to permanent discontinuation, irrespective of recovery time, unless otherwise specified. Exceptions would include nausea/vomiting/diarrhea which can be controlled by medications and/or asymptomatic electrolyte imbalances which can be corrected. In addition, in most instances, patients that experience a prolonged treatment interruption because of an adverse event and/or a grade 3 adverse event will decrease the dose of study drug after their recovery (see specific tables for dose adjustment guidelines). Furthermore, patients requiring >1 dose reduction for APR-246 will be permanently discontinued from study drug. Patients who permanently discontinue all study drugs should have follow-up within 30 days after discontinuation of all study treatment or resolution of the AE to \leq grade 1, whichever occurs first, that includes all study assessments appropriate to monitor the event.

4. DLT Definition

Patients will be evaluated for DLTs during the lead-in phase and first cycle of combination therapy, i.e., 6 weeks for purpose of deciding the dose for next cohort (see Table 1) but DLTs will continue to be evaluated and reported through all cycles on study. DLT is defined as follows based on the CTCAE v 4.03:

- Treatment related non-hematological CTCAE grade 3-4 toxicity that lead to dose modification or withdrawal.
- Absolute neutrophil count (ANC) not recovering to $>500/\mu\text{L}$ by day 42 of a cycle in the absence of active leukemia/myelodysplasia will be considered a DLT.
- Grade 3 metabolic/electrolyte abnormalities that are not clinically significant, and are adequately controlled within 72 hours are not to be considered DLT.
- Grade 3 nausea/vomiting/diarrhea or CNS toxicity that does not resolve within 28 days despite treatment interruption and maximum medical therapy will be considered a DLT.

5. Criteria for APR-246 dose modifications (Phase 2)

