For patients who do not tolerate APR-246 initial dosing schedule, dose adjustment is permitted in order to allow the patient to continue on study drug. In general, doses should not be reduced

for grade 1 toxicities or grade 2 toxicities with resolution on dose interruption (see Table 8), but treatment to control symptoms should be provided as appropriate. The starting dose level of APR-246 will be based on the recommended phase 2 dose (RP2D) upon completion of the phase 1 component of the trial (see Table 5). If dose level 3 (i.e. 100mg/kg LBW) is the RP2D based on the phase 1b part of the trial, the dosing will be changed to an equivalent fixed dose regimen of 4500mg/patient. For each patient, a maximum of 2 dose reductions of APR-246 (as outlined in Table 7) will be allowed. Patients requiring an additional dose reduction will be discontinued from treatment with APR-246. Patients whose treatment is interrupted or permanently discontinued due to an adverse event or clinically significant laboratory value must be followed up within 30 days, or resolution of the AE to \leq grade 1, whichever occurs first, that includes all study assessments appropriate to monitor the event.

Table 7 Dose reduction steps for APR-246 (Phase 2 only)

APR-246 dose levels and dose reduction*	
Starting dose level	RP2D days 1-4 of each cycle
Dose level – 1	RP2D-500mg fixed dose days 1-4 of each cycle**
Dose level – 2	RP2D-1000mg fixed dose days 1-4 of each cycle**

*Dose reduction should be based on the worst preceding toxicity.
 ** = If a dose reduction below dose level –2 is required, the patient should be permanently discontinued from APR-246

Guidelines for dose modification and dose interruption for toxicities suspected to be related to APR-246 are described in Table 8.

Table 8 APR-246 – recommended dose modifications and criteria for treatment interruption and re-initiation with treatment-related adverse events

These changes must be recorded on the Dosage Administration Record CRF.

Worst toxicity (CTCAE 4.03 Grade)**	Dose Modifications for APR-246
HEMATOLOGICAL (only applicable for patients with normal baseline absolute neutrophil count (ANC) and platelets)	
Neutropenia (ANC)	
Severe Febrile neutropenia	Omit dose until resolved, then ↓ 1 dose level

Worst toxicity (CTCAE 4.03 Grade)**	Dose Modifications for APR-246
(ANC < 0.5 x 10 ⁹ /L, temperature of ≥ 38 °C and ICU admission)	
Thrombocytopenia	

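### For a Phase 2 patient who needs a second APR-246 dose reduction, Section 10.3 requires permanent discontinuation while Section 10.5 and Table 7 allow treatment to continue

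*Combined protocol and SAP*

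**What the plan says.** Four places in the protocol bear on how many times APR-246 may be reduced.

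- **Section 10.3** (treatment interruption and discontinuation): "patients requiring >1 dose reduction for APR-246 will be permanently discontinued from study drug". The sentence names no phase and no type of toxicity.
- **Section 10.5** (dose modification criteria, headed as applying to Phase 2): "For each patient, a maximum of 2 dose reductions of APR-246 (as outlined in Table 7) will be allowed". It continues: "Patients requiring an additional dose reduction will be discontinued from treatment with APR-246".
- **Table 7** (labelled Phase 2 only): two steps below the starting dose. The second, dose level -2, is "RP2D-1000mg fixed dose days 1-4 of each cycle". The footnote says that if a reduction below that level is required, "the patient should be permanently discontinued from APR-246".
- **Section 6, Phase 2 dose table**: a first reduced level of 4.0 g per day and a second, DL-2, of "APR-246 3.5 g/patient/day", each with its loading and maintenance split. This table states no discontinuation rule.

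**The concern.** A Phase 2 patient at dose level -1 who needs one more reduction must be taken off permanently under Section 10.3. The same patient may continue at dose level -2 under Section 10.5 and Table 7. Both instructions are current and directive, so a site that follows one departs from the other.

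In a multi-institution trial this matters in three ways:

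- **Exposure.** Time on APR-246 after a second toxicity may depend on which paragraph the site consulted.
- **Safety reporting.** Section 15.3 reports adverse events leading to treatment discontinuation. One toxicity history counts as such an event under Section 10.3 and need not under Section 10.5.
- **Secondary efficacy set.** The second analysis in Section 15.4 is restricted to patients who complete at least three cycles and the first on-treatment marrow. A patient stopped early under Section 10.3 could fall outside that set, while one kept on at level -2 could remain in it.

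A smaller ambiguity lies in the same sentence. Section 10.3 discontinues from *study drug*, whereas Section 10.5 and the Table 7 footnote discontinue from APR-246. Whether azacitidine also stops under Section 10.3 is not clear.

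**Working it through.** The point is a conflict of text, so the main check sets the rules side by side.

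| Reductions needed by a Phase 2 patient | Section 10.3 | Section 10.5 and Table 7 |
|---|---|---|
| 1 | continue, reduced | continue at level -1 |
| 2 | permanently discontinue | continue at level -2 |
| 3 | already off drug | permanently discontinue APR-246 |

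The rules differ only in the second row, but there they are opposite.

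**Is level -2 a genuine step in the plan?** Take the fixed Phase 2 dose of 4500 mg, which applies if dose level 3 is the RP2D, and the Table 7 decrements of 500 mg and 1000 mg:

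- Level -1: 4500 − 500 = 4000 mg. Section 6 split: 1.33 + 2.67 = 4.0 g.
- Level -2: 4500 − 1000 = 3500 mg. Section 6 split: 1.16 + 2.34 = 3.5 g.
- Starting level: 1.5 + 3.0 = 4.5 g.

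Section 6 and Table 7 agree on a two-step ladder. If Section 10.3 is applied as written, the second step can never be used.

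**How many patients?** The documents give no frequency of second reductions, so a range of 5% to 15% is assumed. The denominator is the Phase 2 portion, up to 39 evaluable patients (Section 15.1). The 45 in the Simon design includes Phase 1b patients treated at the MTD, to whom Table 7 does not apply.

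- 0.05 × 39 = 1.95, about 2
- 0.15 × 39 = 5.85, about 6

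**Does the primary design change?** Exact binomial calculation of the two-stage rule (24 patients, continue with 6 or more CRs; 45 patients, success with 14 or more):

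| Quantity | Plan | Recomputed |
|---|---|---|
| Type I error at a 20% CR rate | 0.05 | 0.048 |
| Power at a 40% CR rate | 90% | 0.900 |
| Probability of early termination at a 20% CR rate | 0.66 | 0.656 |

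The plan's figures reproduce, and none of them depends on the dose-reduction rule.

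**The case against.** The best defence is a split by phase. Section 10.5 and Table 7 are labelled Phase 2, so Section 10.3 might be meant for Phase 1b, or as a general rule that the Phase 2 rule overrides. Part of this stands: for Phase 1b patients only Section 10.3 sets a limit, and there is no contradiction for them. The defence does not remove the conflict in Phase 2. Section 10.3 states no such limit, and its preceding sentence sends the reader to the dose-adjustment tables. Tables 7 and 8 both sit under the Phase 2 heading of Section 10.5. The qualifier allowing for exceptions in Section 10.3 belongs to the grade 4 rule, not to this one.

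A second defence is oversight. Under Section 11 the principal investigator reviews serious adverse events and the resulting delays or reductions. Section 17.8 provides for biweekly review of adverse events, and dose changes must be recorded on the dosing CRF. This makes practice traceable and may bring sites into line. It does not settle which text governs, and it is why the supportable claim is that sites may differ, not that they will.

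A reader might also infer that the conflict puts the primary conclusion at risk, because success turns on 13 versus 14 CRs. The documents do not support that:

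- The ITT analysis in Section 15.4 keeps every treated patient regardless of treatment duration.
- The endpoint is achieving CR, so stopping drug afterwards does not undo a CR.
- An end-of-treatment marrow and response assessment are planned where feasible.
- Only a patient who needs a second reduction before reaching CR, and who would then have reached CR at level -2, could alter the count. Nothing in the documents sizes that subset, which is part of the 2 to 6 above.

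**Conclusion.** The contradiction is real and confined to Phase 2 patients who need a second APR-246 reduction. For them the protocol gives opposite instructions on permanent discontinuation after toxicity, and a site cannot comply with both. The number affected is unknown. The figure of about 2 to 6 rests entirely on the assumed 5% to 15% and on a full Phase 2 accrual of 39.

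The consequences that the documents support are variation in exposure, in counts of discontinuations due to adverse events, and possibly in membership of the three-cycle evaluable set. It would go too far to say that the trial evaluates more than one regimen: the starting dose, the schedule and the first reduction step are common to both rules. No effect on the Simon design or on the CR decision is shown. The reason to correct the text is that it is a patient-safety instruction that contradicts itself.

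**What to change.** Reconcile Section 10.3, Section 10.5 with Table 7, and the Section 6 Phase 2 dose table in one amendment:

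1. State one maximum number of APR-246 reductions and one discontinuation trigger, identically in every place. The clinical team decides which.
2. If Phase 1b and Phase 2 are meant to differ, say so in Section 10.3.
3. Say whether *study drug* in Section 10.3 means APR-246 alone or also azacitidine.
4. For any patient already treated who needed a second reduction, record which rule was applied, so that exposure, discontinuations and membership of the three-cycle set can be interpreted.

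The cost is amendment wording and a short look-back through the dosing records. Sample size, decision boundaries and planned analyses stay as they are.

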4. PATIENT SELECTION

4.1. Eligibility criteria

Inclusion Criteria:

1. Patient has signed the Informed Consent (ICF) and is able to comply with protocol requirements
2. Patient has adequate organ function as defined by the following laboratory values:
 - a. Serum creatinine ≤ 2 x upper limit of normal (ULN)
 - b. Total serum bilirubin < 1.5 x ULN or total bilirubin ≤ 3.0 x ULN with direct bilirubin within normal range in patients with well documented Gilbert's Syndrome or

hemolysis or who required regular blood transfusions

- c. Alanine aminotransferase (ALT) and aspartate aminotransferase (AST) $< 2.5 \times \text{ULN}$
3. Age ≥ 18 years at the time of signing the informed consent form
4. Documented diagnosis of myelodysplastic syndrome (MDS), MDS/ myeloproliferative neoplasm (MPN), chronic myelomonocytic leukemia (CMML) by WHO criteria or AML with 20-30% myeloblasts (refractory anemia with excess blasts in transformation (RAEB-T) by French-American-British (FAB) criteria)
5. Documentation of a *TP53* gene mutation by NGS based on central or local evaluation
6. Revised International Prognostic Scoring System (IPSS-R) criteria for Intermediate, High-risk or Very High-risk.
7. An Eastern Cooperative Oncology Group (ECOG) performance status score of 0, 1, or 2 is required.
8. If of childbearing potential, negative pre-treatment urine or serum pregnancy test.
9. If of childbearing potential (males and females), willing to use an effective form of contraception such as latex condom, hormonal birth control, intrauterine device or double barrier method during chemotherapy treatment and for at least six months thereafter.

Exclusion Criteria

1. Patient has a known history of HIV or active hepatitis B or active hepatitis C infection (testing not mandatory).
2. Patient has any of the following cardiac abnormalities (as determined by treating MD):
 - a. Symptomatic congestive heart failure
 - b. Myocardial infarction ≤ 6 months prior to enrollment
 - c. Unstable angina pectoris
 - d. Serious uncontrolled cardiac arrhythmia
 - e. QTc ≥ 470 msec
3. Concomitant malignancies or previous malignancies with less than a 1-year disease free interval at the time of signing consent. Patients with adequately resected basal or squamous cell carcinoma of the skin, or adequately resected carcinoma in situ (e.g. cervix) may enroll irrespective of the time of diagnosis.
4. Prior exposure to azacitidine, decitabine or investigational hypomethylating agent.

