10. DOSING DELAYS/MODIFICATIONS

1. Dose modification and dose delay

For patients who do not tolerate the protocol-specified dosing schedule, dose adjustments are permitted in order to allow the patient to continue the study treatment. All dose modifications, interruptions or discontinuations must be based on the worst preceding toxicity as graded by the

NCI Clinical Toxicity Criteria (NCI-CTCAE version 4.03). Once a dose has been reduced during a treatment cycle, re-escalation will not be permitted during any subsequent cycle (with exception of CNS events, see 10.2). If the administration of APR-246 is interrupted for reasons other than toxicity, then treatment with the respective study drug may be resumed at the same dose. The same provision applies if the patient experienced an unacceptable toxicity not specifically described in Table 8 provided that this toxicity resolved to \leq CTCAE grade 1, unless otherwise specified.

2. Treatment of adverse events of the CNS related to APR-246

If a patient reports any clinical adverse event of any grade during the administration period of APR-246 that could be considered to originate from the central nervous system (e.g., dizziness, vertigo, nausea) then the following medications may be used (Table 6). Prochlorperazine is not required to be taken at any point but is per discretion of the treating physician.

Table 6. Adjuvant Medications for use with APR-246

Indication	Supportive Measure
Central Nervous System (CNS) symptoms (Treatment and Prevention)	Prochlorperazine 10 mg orally tid as needed Start Day -1 prior to APR-246 administration
Persistent CNS symptoms	Diphenhydramine 50 mg IV (or similar anti-histamine)

Prochlorperazine 10 mg orally tid (three times daily) to continue until end of Day 4 of the cycle. When used prophylactically for future treatment, start the day prior to Day 1 administration of APR-246. If during the infusion the patient continues to remain symptomatic, intravenous administration of diphenhydramine 50 mg (or similar anti-histamine) should be considered. If prophylactic prochlorperazine results in \leq grade 1 CNS toxicity on subsequent doses, re-escalation to previous dose level can occur with the next cycle at the discretion of the study investigator.

3. Treatment interruption and treatment discontinuation

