Grade 4 (PLT < 25 x 10 ⁹ /L) AND major bleeding event	Permanently discontinue patient from APR-246
RENAL	
Serum creatinine	
Grade 1 (< 2 x ULN)	Maintain dose level
Grade 2 (2 – 3 x ULN)	Omit dose until resolved to ≤ grade 1, then: If resolved in ≤ 7 days, then maintain dose level If resolved in > 7 days, then ↓ 1 dose level
Grade 3 (> 3.0 – 6.0 x ULN)	If resolved in ≤ 7 days, then ↓ 1 dose level If resolved in > 7 days, discontinue patient from APR-246
Grade 4 (> 6.0 x ULN)	Permanently discontinue patient from APR-246
HEPATIC	
Bilirubin	
(*for patients with Gilbert Syndrome, these dose modifications apply to changes in direct bilirubin only) will be fractionated if elevated	
Grade 1 (> ULN - 1.5 x ULN)	Maintain dose level with LFTs* monitored as per protocol
Grade 2 (> 1.5 - 3.0 x ULN) with ALT or AST ≤ 3.0 x ULN	Omit dose until resolved to ≤ Grade 1, then: If resolved in ≤ 7 days, then maintain dose level If resolved in > 7 days, then ↓ 1 dose level
Grade 3 (> 3.0 - 10.0 x ULN) with ALT or AST ≤ 3.0 x ULN	Omit dose until resolved to ≤ Grade 1, then: If resolved in ≤ 7 days, ↓ 1 dose level If resolved in > 7 days, discontinue patient from APR-246
Grade 4 (> 10.0 x ULN)	Permanently discontinue patient from APR-246
AST or ALT	
Grade 1 (> ULN – 3.0 x ULN)	Maintain dose level with LFTs* monitored per protocol
Grade 2 (> 3.0 - 5.0 x ULN) without total bilirubin elevation to > 2.0 x ULN	Omit dose until resolved to ≤ Grade 1, then If resolved in ≤ 7 days, then maintain dose level If resolved in > 7 days, then ↓ 1 dose level
Grade 3 (> 5.0 - 20.0 x ULN) without total bilirubin elevation to > 2.0 x ULN	Omit dose until resolved to ≤ Grade 1, then If resolved in ≤ 7 days, then maintain dose level If resolved in > 7 days, then ↓ 1 dose level

Worst toxicity (CTCAE 4.03 Grade)**	Dose Modifications for APR-246
Grade 4 (> 20.0 x ULN) without bilirubin elevation to > 2.0 x ULN	Permanently discontinue patient from APR-246
*(LFTs include albumin, ALT, AST, total bilirubin (fractionated if total bilirubin > 2.0 x ULN), alkaline phosphatase.	
CNS – dizziness, dyskinesia and ataxia	
Grade 1	Maintain dose level
Grade 2	If resolved with medical therapy (e.g., prochlorperazine or antihistamines), continue same dose level If not resolved despite treatment interruption and maximal medical therapy, stop infusion and ↓ 1 dose level for subsequent dose

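### Table 8 has no action row for bilirubin >2.0–10.0 x ULN with both ALT and AST >3.0 x ULN, and the general rules can then be milder than the row for bilirubin alone

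*Combined protocol and SAP*

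**What the plan says.** Table 8 sits under Section 10.5, which covers Phase 2, and deals with toxicity suspected to be related to APR-246.

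- **Bilirubin rows.** Two rows carry an enzyme condition: "Grade 2 (> 1.5 - 3.0 x ULN) with ALT or AST ≤ 3.0 x ULN" and "Grade 3 (> 3.0 - 10.0 x ULN) with ALT or AST ≤ 3.0 x ULN". Grade 2 means the same dose if resolved within 7 days and one level down if later. Grade 3 means one level down within 7 days and discontinuation if later. The grade 4 row (>10.0 x ULN) is unconditional and discontinues.
- **AST/ALT rows.** Grades 2, 3 and 4 each carry a bilirubin condition, as in "Grade 3 (> 5.0 - 20.0 x ULN) without total bilirubin elevation to > 2.0 x ULN". Grades 2 and 3 both mean the same dose within 7 days and one level down if later. Grade 4 discontinues.
- **Gilbert exception.** It stands under the Bilirubin heading only: "for patients with Gilbert Syndrome, these dose modifications apply to changes in direct bilirubin only".
- **Section 10.1.** Modifications "must be based on the worst preceding toxicity as graded by the" CTCAE scale. Treatment interrupted for reasons other than toxicity may resume at the same dose, and "The same provision applies if the patient experienced an unacceptable toxicity not specifically described in Table 8" once it has resolved to grade 1 or less, subject to anything specified elsewhere.
- **Section 10.3.** A grade 3 event or a prolonged interruption leads in most cases to a lower dose, with a pointer to the tables. No number of days defines prolonged. Related non-hematologic grade 4 events, and dose delays over 28 days, mean permanent discontinuation.
- **Section 10.5.** Grade 2 events that resolve on interruption generally do not call for a reduction.
- **Section 4.1, inclusion 2b.** It admits "total bilirubin ≤ 3.0 x ULN with direct bilirubin within normal range in patients with well documented" Gilbert's Syndrome, or with "hemolysis or who required regular blood transfusions".

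**The concern.** The bilirubin rows and the enzyme rows each step aside when the other abnormality is present, and no combined row takes over. Bilirubin and both enzymes raised together is a more worrying liver picture than either alone, yet it is the one without an instruction.

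A patient with bilirubin 4, ALT 8 and AST 2.5 x ULN who recovers after 10 days falls, read literally, in the grade 3 bilirubin row and stops APR-246. If AST also rises to 6, that row no longer applies, and Section 10.3 usually only lowers the dose. At stake are the safety of the individual patient and consistency between sites in a multi-institution trial.

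**Working it through.** The plan states no figure on this point, so there is none to reproduce. The check is an enumeration of the rows quoted above.

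**Step 1: coverage.** The row conditions were applied to 10 bilirubin values (0.9 to 10.1 x ULN) crossed with 8 values each of ALT and AST (0.9 to 20.1 x ULN). The bilirubin rows were taken as satisfied if at least one enzyme is ≤3.0. Cells with bilirubin >2.0–10.0 and both enzymes >3.0 number 5 × 5 × 5 = 125. All 125 have no row, and no other abnormal cell is uncovered. If the condition means both enzymes ≤3.0, the gap widens to either enzyme >3.0.

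**Step 2: what other text settles.** Bilirubin >10.0 has its own row. Enzymes >20.0 are grade 4 and stop under 10.3. The 28-day limit is on dose delay, not recovery time. For an event found at the day 8 bloods, the next dose is due on day 29, so a 28-day delay ends on day 29 + 28 = 57, which is 57 − 8 = 49 days after detection. What stays open is grade 2–3 events within that delay limit.

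**Step 3: eight cases.** Bilirubin grade 2 (>2.0–3.0) or 3, higher enzyme grade 2 or 3, recovery ≤7 or >7 days: 2 × 2 × 2 = 8. Actions are ordered same < down < stop. The general rule is 10.1 read with 10.3, for a patient with no prior reduction, and is compared with the stricter of the two isolated rows.

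| Bilirubin | Enzyme | Recovery | Bilirubin row | Enzyme row | 10.1 with 10.3 | Result |
|---|---|---|---|---|---|---|
| 2 | 2 | ≤7 d | same | same | same | equal |
| 2 | 3 | ≤7 d | same | same | down | stricter |
| 3 | 2 | ≤7 d | down | same | down | equal |
| 3 | 3 | ≤7 d | down | same | down | equal |
| 2 | 2 | >7 d | down | down | same or down | unsettled |
| 2 | 3 | >7 d | down | down | down | equal |
| 3 | 2 | >7 d | stop | down | down | milder |
| 3 | 3 | >7 d | stop | down | down | milder |

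Totals: 2 milder, 1 unsettled, 1 stricter, 4 equal. In the unsettled case 10.5 points to the same dose (milder), while 10.3 points to a decrease if more than 7 days counts as prolonged (equal). The count is therefore 2 to 3 of 8.

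**Step 4: other readings.**

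- 10.1 alone gives the same dose in all eight. The stricter row exceeds that in 2 cases at ≤7 days and 4 at >7 days, so 6 of 8 are milder.
- If the worst-toxicity sentence is taken to import the isolated bilirubin action, 0 of 8 are milder, because that action is at least as strict as the enzyme action in all eight.
- After one prior reduction the count stays 2 under the two-reduction limit in 10.5. It falls to 0 under 10.3, which stops APR-246 at more than one reduction. After two prior reductions (10.5 only) it is 0. The unsettled case remains throughout.

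**Step 5: dose.** If the RP2D is the 4.5 g fixed dose, one level down is 4.0/4.5 = 89% and two levels 3.5/4.5 = 78%. Either is milder than stopping.

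**Step 6: baseline.** A Gilbert patient may enrol with total bilirubin 2.5 x ULN and normal direct bilirubin. If both enzymes later rise above 3.0, the bilirubin rows, read on direct bilirubin, do not apply. The enzyme rows are excluded because they use total bilirubin. An enzyme-only event then has no row.

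**The case against.** The best defence is the worst-toxicity rule. Section 10.1 states it, the Table 7 footnote repeats it, and Table 8's first column is headed accordingly. Section 10.3 sends the reader to the tables, and its decrease is hedged, so it does not forbid stopping. A site could reasonably apply the isolated bilirubin action, and then nothing is milder. This stands as a possible reading. But the sentence only says which toxicity governs; it does not waive the enzyme condition in the bilirubin rows, which excludes this pattern.

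Safeguards also stand. Table 8 is labelled as recommended. Section 9c requires stopping when the investigator judges continued participation an unacceptable risk. The monitoring plan in Section 17.8 has the principal investigator and study team review grade 3 and higher events every two weeks, which covers 6 of the 8 cases, including both milder ones. These limit the harm but do not tell a site which dose to give.

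A reader might infer that the plan returns these patients to full dose, the 6-of-8 result. The documents do not support this: 10.1 yields to anything specified elsewhere, and 10.3 does specify a decrease for grade 3 events in most instances.

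**Conclusion.** The gap holds on the literal text. Its consequence depends on the reading: 2 to 3 of 8 cases milder under 10.1 with 10.3, and 0 to 6 of 8 across all readings. The firm part of the 10.1-with-10.3 result is grade 3 bilirubin recovering in more than 7 days, which gets a decrease where bilirubin alone means discontinuation.

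This assumes no prior reduction, a dose delay of at most 28 days, and the 10.3 decrease taken as the default and as one level. If that decrease is read as optional, the 2 milder cases remain and 5 of 8 become unsettled.

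The eight cases are not weighted. The documents give no incidence, so 2 of 8 is not a share of patients. Nor should a reader infer any threat to the efficacy result: the CR endpoint and the Simon rule are unaffected. This is a modest safety correction worth making.

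**What to change.** Add one Table 8 row for bilirubin >2.0–10.0 x ULN with the higher of ALT and AST >3.0–20.0 x ULN:

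- Omit the dose until resolution to grade 1 or less, or to baseline for a patient enrolled with bilirubin above grade 1.
- Then take at least the isolated bilirubin action. Grade 2: ≤7 days maintain, >7 days down one level. Grade 3: ≤7 days down one level, >7 days discontinue.
- If either enzyme is grade 3, reduce by at least one level.
- If either enzyme is >20.0 x ULN, discontinue permanently whatever the bilirubin.

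Naming the higher enzyme matters: a condition on one enzyme or the other could admit a patient with one grade 4 value and weaken the stop that 10.3 now gives.

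In the two existing bilirubin rows, require both ALT and AST to be ≤3.0 x ULN. State that for Gilbert Syndrome the bilirubin limits in the new row and in the AST/ALT rows refer to direct bilirubin. State also that the 10.1 provision for toxicities not described in Table 8 does not apply to this pattern. The sponsor's safety physician may choose a stricter action.

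The cost is one row, one word in each of two rows and two sentences in an amendment. ALT, AST and total bilirubin are already collected, and Table 8 already calls for fractionation when bilirubin is elevated. The downside is that a few patients may be reduced or stopped who could otherwise have resumed at the same or a reduced dose.
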